5.6 Household Contacts

Household contacts 18 years or older will be asked to self-collect oral swabs in the same manner and same daily schedule as the study participant. Provision of the oral swabs will be considered implied consent, waiving the need for consent documentation.

5.7 Data collection.

Research coordinators and/or investigators will collect data and record them on paper and/or electronic CRF provided by the Data Coordinating Center (DCC). Data quality will be monitored by clinical data managers at the DCC. Note that given concerns for contagion during the pandemic, coordinators will practice “no-touch” practices for data collection and entry.

6.0 Analysis and interpretation of data.

A formal statistical analysis plan (SAP) will be written and finalized before the conclusion of enrollment and prior to the beginning of data analysis. The principles of this SAP are outlined here.

We note that in the unique circumstances of this trial setting, it is possible that information may become available that would lead to modifications of prespecified analysis. A hypothetical example would be evidence from multiple global studies that a particular underlying condition is strongly associated with outcomes such as shedding or hospitalization rates in response to hydroxychloroquine. In such circumstances, a modification to this study's analysis plan could

UTAH One (Understanding Treatment And Health in the Ongoing coroNa Epidemic): A Hydrochloroquine Outpatient Study

be considered, if possible with the investigators blinded to the effect of the modification on the analysis, and in consultation with the DSMB. If the statistical analysis plan were to be modified, the analytic plan would be updated, with the previous version retained, and the modification explicitly noted in the presentation of the trial results.

The primary prespecified analysis for efficacy is a comparison of duration of viral shedding during the first 14 days after randomization between the two treatment arms. For each participant, this outcome will be defined as the number of days until an oral swab sample shows no shedding, as confirmed by a sample from the subsequent day. Thus, for example, a participant with their first negative samples on days 7 and 8 would be treated as having stopped shedding on Day 7. The requirement for confirmation will be waived for patients who are negative for shedding on Day 14.

Due to the nature of the data collected over a 14-day interval, and uncertainty about the distribution of shedding duration and the resulting hazard function, our primary analysis will apply the stratified log-rank test to compare the distribution of shedding duration between the hydroxychloroquine and control groups, with administrative right censoring at day 14. The primary analysis will be conducted using a 2-sided $\alpha=0.05$. The log-rank test will be stratified by the age group randomization stratum. The Efron approach will be used to account for tied shedding duration times. Kaplan-Meier curves will summarize the shedding time distributions in the two randomized groups.

Special handling will be required in our primary analysis of shedding duration for periods in which patients are hospitalized because swabs will not be obtained during hospitalizations. In our primary analysis, we will apply a last value carried forward imputation approach during hospitalization, and assume continued viral shedding during hospitalizations for patients whose last pre-hospitalization assessment is positive. A sensitivity analysis will right censor follow-up on the day of hospital admission. These two analyses represent the range of plausible scenarios for shedding during hospitalization under the assumption that any association between hospitalization and shedding must be positive; i.e., conditional on past history, the risk of viral shedding on any given day is at least as large for hospitalized as for non-hospitalized patients. We expect a relatively small proportion of subjects to be hospitalized, limiting the impact of assumptions concerning shedding during hospitalizations on the primary analysis. Additional sensitivity analyses, including analyses in which the end date of shedding is modeled as a latent variable will be considered.

Quantification of the magnitude of “treatment effect”, and indeed the interpretation of the trial results, will depend on the specific patterns of the shedding distribution. For example, in the unexpected scenario where the cumulative incidence curves for the ending of shedding actually cross during the 14-day evaluation period, the treatment arm with lower 14-day shedding rate would likely be preferred regardless of any shorter-term benefit observed in the other arm. Assuming, however, that the assumption of proportional hazards is found to be consistent with the data, the effect of the treatment will be expressed as a hazard ratio with 95% confidence interval. We will also report the differences between the randomized groups in truncated mean shedding duration to 14 days and in median shedding duration with 95% confidence intervals based on estimates derived from Kaplan-Meier curves.

The comparison of proportion of patients hospitalized by day 14 between the randomized hydroxychloroquine and placebo groups will be performed with a two-sided Mantel-Cochran-Haenszel test stratifying by the age categories as used for randomization, with 2-sided

UTAH One (Understanding Treatment And Health in the Ongoing coroNa Epidemic): A Hydrochloroquine Outpatient Study

alpha=0.05. In the unlikely event that some patients die within 14 days after randomization without being hospitalized, these patients will be assigned to the hospitalization category in the analysis. Results will be presented as relative risks with 95% confidence intervals within each age stratum, and then pooled across strata.

The average symptom level for assessment days 1 through 15 will be compared between treatment groups, as described in the Statistical Analysis Plan. The duration of COVID-19 attributable symptoms through assessment day 15 will be summarized graphically across evaluation time points using Kaplan-Meier curves, and compared between randomized groups by applying the log rank test with stratification by the age randomization strata. Participants who are hospitalized by assessment day 15 will be treated as having symptoms each day they are in the hospital. Follow-up time will be right censored at assessment day 15

Our main analysis of adult household contact viral acquisition will be restricted to households with at least 2 adults for which no other adult besides the index study subject tests positive for COVID-19 at baseline. We will evaluate the effect of the hydroxychloroquine intervention on the risk of adult household viral acquisition by applying a Mantel-Cochran-Haenszel test stratifying by the randomization age categories and total number of adults within the household. Results will be presented as relative risks with 95% confidence intervals within each stratum, and then pooled across strata. A secondary analysis will assess the effect of treatment arm on rate of household viral acquisition rates averaged across all adults within the household by using a modified Poisson regression model incorporating correlation between participants in the same household, and controlling for age category and number of household members.

The Statistical Analysis plan will detail additional analyses to be performed, including additional exploratory analysis as well as reporting of six-month outcomes among participants.

Safety—already well established in studies of thousands of patients and in post-marketing surveillance—will be assessed through counts (proportions) of adverse events, with special attention to those listed in the package insert for hydroxychloroquine and careful investigation of any SUSARs. As noted elsewhere in this protocol, safety data will be reported to the trial DSMB after every (approximately) 100 subjects have been enrolled in the trial.

We do not anticipate applying formal stopping rules for either efficacy or futility in this trial. It is expected that the trial will remain open for up to 12 months, as the cyclic nature of the illness is not well understood. Thus, if enrollment is not accomplished in this first wave of infection, the trial will not be suspended for futility, anticipating that subsequent waves may occur and enable full enrollment.

6.1 Power and sample size analysis

For a survival analysis, statistical power is readily expressed as a function of the number of events or event rate. Table 2 below shows minimum increases in the hazard rate due to hydroxychloroquine detectable with 80% power, under different overall event rates by 14 days in the trial (calculations done in PASS assuming a conventional proportional hazards model with treatment arm as a single predictor, using a two-sided test with alpha=0.05). With 400 enrolled participants, within our expected range of observed shedding rates, we expect the trial to have substantial power to detect a treatment effect if hydroxychloroquine increases the “successful

UTAH One (Understanding Treatment And Health in the Ongoing coroNa Epidemic): A Hydrochloroquine Outpatient Study

outcome" rate (at each timepoint) 1.4-fold or greater compared to the rates observed with placebo.

Table 2. Minimum Increase in Hazard Rate Yielding 80% Power with 2-sided $\alpha=0.05$, with N=400 randomized and evaluable subjects

Assumed Overall Rate of No Shedding by 14 Days	Minimum Hazard Ratio for "No Shedding" Outcome due to Hydroxychloroquine for which Power is 80%
50%	1.49
55%	1.46
60%	1.44
65%	1.42
70%	1.40
75%	1.38
80%	1.37

7.0 Human Subjects Considerations.

If a person without insurance is hospitalized for illness related to COVID-19, he or she is eligible for emergency Medicaid. This is beyond usual Medicaid eligibility and related to special rules related to COVID-19 illness. In 2019, the United States government issued new rules in the form of an executive order restricting the ability for immigrants who use public benefits, including Medicaid, from obtaining permanent residency. For many individuals who are not citizens or permanent residents of the United States—whether they are documented or not—this has made them reluctant to use public programs for which they are eligible, including Medicaid and COVID-19 related health benefits.

In order to uphold principle of justice for all research participants, and to ensure that everyone who participates in this study will be appropriately respected for volunteering, we have partnered with U Health to offer participants who are uninsured **and** for whom completing paperwork regarding financial assistance would put them at risk in their judgement, the ability to receive the same level of care for COVID-19 as other people, should this be needed during their participation.

All participants will be provided with information during their first visit by the study nurse that if they require hospitalization, are uninsured, and if in their judgement completing paperwork regarding financial assistance would put them at risk, they should, upon presenting to a U Health emergency department, identify themselves to the registrar and financial counselor. The financial counselor will identify their participation in the electronic health record and note this in the hospital billing system.

Participants will be provided with a card identifying them as study participants and with instructions on it so as to remind them of what to do if they need to be hospitalized. They will also be provided with a handout to keep at home in case they are unable to speak to the financial counselor and hospital rules restrict visitors so the person contacted regarding the patient at home has the same information.

UTAH One (Understanding Treatment And Health in the Ongoing coroNa Epidemic): A Hydrochloroquine Outpatient Study

7.1 Institutional Review Board oversight.

Institutional Review Board (IRB) approval is required and will be secured before any subject is enrolled at the study site. The DCC will not enable access to the electronic data capture or randomization systems until IRB documentation is received.

7.2 Informed consent.

Informed consent will be obtained from participants prior to randomization. Proxy consent will not be used. Informed consent will be obtained without an original paper signature because of the contagious nature of the virus. Adult household contacts who agree to provide daily swabs are presumed to be consenting, and documentation of consent will be waived for them.

7.3 Potential risks

Risks associated with participation in this study include risks associated with HCQ administration and potential loss of confidentiality.

The package insert for HCQ lists visual impairment, cardiac impairment, QTc prolongation, worsening of psoriasis or porphyria, proximal myoneuropathy, suicidality, and hypoglycemia. All of these risks are quite rare and where observed are seen after prolonged administration, generally in the range of years. While ocular examinations are recommended after a year (and for acute symptoms), routine ocular examinations have never been recommended for brief duration of therapy. While QTc prolongation has been described with HCQ, it is generally modest, and routine EKG monitoring is not normally practiced even during long-term administration of hydroxychloroquine. HCQ may be associated with prolongation of QTc. We chose a conservative threshold of 500msec as an exclusion criterion after consultation with electrophysiology cardiologists.

7.4 Mitigation of risks

In order to mitigate the risk of prolongation of QTc, we have chosen a conservative exclusion threshold of 500 msec after consultation with electrophysiology cardiologists. Daily assessments will specifically ask about the adverse events listed above on a daily basis. Our eligibility criteria exclude patients with elevated risk of HCQ toxicity, and we have selected dosages in the lower end of the therapeutic range. Further, treatment is restricted to 5 days.

Risk of loss of confidentiality is mitigated by securing all paper materials used by coordinators for data collection, and IT security maintained at the DCC. Direct patient identifiers (names, contact information, medical record numbers) will not be recorded at the DCC, but will be secured at the study sites. The study sites will maintain lists that correlate medical record numbers with study ID numbers recorded in the DCC electronic data capture system.

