Daily assessments (assessment days 1 through 15) will include review for hospitalization and current symptoms. Daily assessments will also explicitly solicit occurrence of rash, symptomatic hypoglycemia, seizure, oxygen supplementation, nausea, vomiting, and impaired vision. Quality of life assessments will be made at baseline, day 28 - 2 days/+2 weeks, and six months - 1

UTAH One (Understanding Treatment And Health in the Ongoing coroNa Epidemic): A Hydrochloroquine Outpatient Study

week/+2 months, using the EQ-5D-5L, PHQ-9, GAD 7, and PLC 5. If the six-month survey is missed during the above outlined window, the study team may attempt to collect it for up to a year following the six-month timepoint.

Participants will be taught how to perform self-collection of oral swabs for SARS-CoV-2 on assessment days 1 – 14 and 28 +/- 2 (considering day 1 as day of study drug delivery). Oral swabs will not be required during hospitalizations, but patients will be asked to provide a swab on the day following discharge from the hospital, even if this occurs after day 28. These will be refrigerated after collection and collected by a courier associated with the study for transport to the central laboratory (ARUP) for testing. Training will be provided with written instructions, video, and discussion with the research coordinators.

Phlebotomy will be performed at day 1, day 7 (+/-2 day), day 28 (+/-2 day) and 6 months- 1 week/+2 months. This will require personal protective equipment (PPE) for the phlebotomy-certified research staff. Note that the 6 months blood draw is being added mid-study, after subjects have been enrolled. Therefore, already enrolled participants will be notified of the 6 months blood draw, provided with a new copy of the consent form, and told that they do not have to participate in the 6 month blood draw. If the six-month blood draw is missed during the above outlined window, the study team may attempt to collect it for up to a year following the six-month timepoint.

Blood samples will be used to assess the immune response to SARS-CoV-2, drug screening, investigation of viral biology, cardiac biomarkers, and development of diagnostic assays. Plasma and peripheral blood mononuclear cells (PBMCs) will be stored in the University of Utah Center for Clinical and Translational Science (CCTS) biospecimen repository. If there is remaining sample after these analyses, they may be used to study other diseases.

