8.0 Adverse Events

Patient safety is central to this study protocol.

8.1 Adverse event reporting. Adverse events will be recorded from randomization through day 14 or hospitalization, whichever occurs first. The following adverse events will be collected in the adverse event case report forms and entered into the DCC electronic data capture system:

- Serious adverse events
- Non-serious adverse events that are considered by the investigator to be related to study drug or study procedures or of uncertain relationship
- Adverse events that lead to permanent discontinuation of the study drug.

The following adverse events will be collected prospectively as part of the study-specific outcomes and do not require additional adverse event reporting with the DCC unless they meet criteria for being serious (defined below):

- Rash
- Symptomatic hypoglycemia
- Seizure
- Cardiac arrhythmias
- Worsening requirement for oxygen supplementation and support
- Nausea/vomiting
- Impaired vision

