Average of Core COVID-19 symptoms There are seven core symptoms: fever, chills, cough, tiredness, shortness of breath, diarrhea, and muscle aches. Symptoms are measured on a 6-point ordinal scale (not experiencing=0, extremely mild=1, mild=2, moderate=3, severe=4, extremely severe=5) at baseline, days 1–15, and day 28. If at most one of the core symptoms is missing for an assessment, the mean of the non-missing core symptoms’ levels for that assessment will be calculated to obtain a symptom burden score. If two or more core symptoms are missing from the assessment, the average symptom level for that assessment will be considered missing.

Adult Household Contact Viral Acquisition This outcome will be analyzed for households with at least two adults for which no other adult besides the index study subject is positive for COVID-19 at baseline and for which the index study subject is in the ITT population. This binary outcome will be at the household level and will be a “yes” if there is a positive swab by one or more adult household contacts for any of the study-administered swabs from days $DayR + 1$ to $DayR + 14$, inclusive. If there are no positive swabs but at least one negative swab, the outcome will be a “no;” otherwise it will be missing. For some additional analyses, an analogous outcome will be defined at the person level for each non-index adult from a household for which no other adult besides the index study subject is positive for COVID-19 at baseline and for which the index study subject is in the ITT population. Another person-level outcome may count the number of study-administered positive swabs from the person and the number of study-administered swabs with a result (e.g., as an offset in a Poisson regression model), again from days $DayR+1$ to $DayR+14$, inclusive.

As exploratory outcomes, the definitions in the previous paragraph will also include study-administered swabs after $DayR + 14$ through $DayR + 30$, if available).

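### Protocol Sections 5.5, 7.3/7.4 and 8.1 give three different adverse event lists: the daily questions claimed in 7.4 are itemised for only 2 of the 7 listed risks, and 8.1 assumes an arrhythmia item that 5.5 lacks

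*Protocol*

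**What the plan says.** Three places in the protocol describe which adverse events are asked about or collected.

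- **Sections 7.3 and 7.4.** Section 7.3 gives the package-insert risks: "visual impairment, cardiac impairment, QTc prolongation, worsening of psoriasis or porphyria, proximal myoneuropathy, suicidality, and hypoglycemia". Section 7.4, which follows directly, says: "Daily assessments will specifically ask about the adverse events listed above on a daily basis".
- **Section 5.5.** This is the only place where the content of the daily adverse event questions is itemised: "Daily assessments will also explicitly solicit occurrence of rash, symptomatic hypoglycemia, seizure, oxygen supplementation, nausea, vomiting, and impaired vision". The same section adds: "Daily assessments (assessment days 1 through 15) will include review for hospitalization and current symptoms".
- **Section 8.1.** "The following adverse events will be collected prospectively as part of the study-specific outcomes", and these need no separate adverse event form unless they are serious. The list is close to that of 5.5 but includes "Cardiac arrhythmias".

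Section 6.0 says that safety will be assessed by counts and proportions of adverse events, with particular attention to those in the hydroxychloroquine package insert. Appendices 1 and 2 schedule a daily adverse event review, which Appendix 1 labels as active. Neither appendix says what it asks.

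**The concern.** Section 7.4 tells the reader, in the human-subjects part of the protocol, that named drug risks are asked about every day. If the instrument does not contain the questions, that assurance is not met as written, and a low or zero count for those risks says little.

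The cardiac item matters most, because two sections each assume that the other captures it. Section 8.1 takes non-serious arrhythmias off the adverse event form because they are captured elsewhere, and the daily list in 5.5 does not capture them. Section 8.2 treats deaths related to arrhythmia as an expected complication of study drug. Neither appendix schedules an ECG, so asking about symptoms is the main visible route to non-serious cardiac events on treatment.

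Masking adds to this. SAP Section 3.3 says that the placebo is not indistinguishable from the active drug and that coordinators are not blinded. Events without a fixed question are more open to reporting that differs between arms.

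**Working it through.** No statistical figure is involved. The check is an item-by-item match of the Section 7.3 list against the other lists.

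| Section 7.3 entry | Item in 5.5? | Item in 8.1? | Other coverage in the documents |
|---|---|---|---|
| Visual impairment | Yes | Yes | – |
| Cardiac impairment | No | In part (arrhythmias) | Shortness of breath in the daily symptom score; prior ventricular arrhythmia excluded |
| QTc prolongation | No | No | Needs an ECG; existing ECGs reviewed before randomization; entry exclusion |
| Worsening psoriasis or porphyria | No (rash is at most a proxy for psoriasis) | No (same) | Both conditions excluded at entry |
| Proximal myoneuropathy | No | No | Muscle aches and tiredness in the daily symptom score |
| Suicidality | No | No | PHQ-9 at baseline, day 28 and six months |
| Hypoglycemia | Yes | Yes | – |

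**Counts**

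1. Strict match of 7.3 to 5.5: 2 of 7 (2 of 8 if psoriasis and porphyria are counted separately).
2. Crediting cardiac arrhythmias in 8.1 against cardiac impairment: 2 + 1 = 3 of 7.
3. Also crediting rash as a proxy for psoriasis: 3 + 1 = 4 of 7. This is the most generous count.
4. In the other direction, 5 of the 7 items in 5.5 (rash, seizure, oxygen supplementation, nausea, vomiting) do not appear in 7.3. The two lists were evidently not drawn from one source.
5. Setting aside QTc (not self-reportable) and psoriasis/porphyria (excluded at entry) leaves 7 − 2 = 5 entries that a participant could report. Section 5.5 itemises 2 of these 5; with 8.1 it is 3 of 5. The two without a specific item on any count are proximal myoneuropathy and suicidality.

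**Section 5.5 against Section 8.1.** With nausea and vomiting counted separately in both, 5.5 has 7 items and 8.1 has 8. The one extra is cardiac arrhythmias.

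**Tracing a non-serious arrhythmia.** Section 8.1 requires no separate form for it. Section 5.5 has no question for it. It is recorded only if the un-itemised daily review or the current-symptom questions happen to bring it out.

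**The daily symptom survey.** SAP Section 5.4 says: "There are seven core symptoms: fever, chills, cough, tiredness, shortness of breath, diarrhea, and muscle aches". These overlap with muscle and cardiorespiratory complaints but do not include weakness, palpitations, fainting or mood.

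**Timing of the mood questionnaire.** The first PHQ-9 after baseline is due at day 28, at the earliest 28 − 2 = day 26. Under Section 8.1, adverse event recording ends at day 14 or hospitalization, so this questionnaire comes at least 26 − 14 = 12 days later.

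**The case against.** A reader might infer that cardiac symptoms, weakness and suicidality are never solicited during dosing and come to light only if a participant volunteers them. The documents do not support that. Section 8.1 lists cardiac arrhythmias as prospectively gathered. Both appendices schedule adverse event review on each day, and Appendix 1 distinguishes this active review from a passive one used during hospitalization. Section 5.5 does not say that its list is exhaustive, and the sentence in 7.4 is itself a commitment to ask. The case report forms are separate documents and cannot be checked here. What is shown is a conflict between sections, not the absence of questions in the field.

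A reader might also infer that the protocol depends on daily questioning alone. It does not. Section 7.4 also names the QTc threshold, risk-based exclusions, dose selection and the five-day limit. Section 7.3 says that the listed risks are rare and, where seen, generally follow years of use. That lowers the expected yield of extra questions, especially for myoneuropathy.

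It can also be said that little in the analysis is at stake. SAP Section 7.5.2 plans descriptive adverse event summaries without formal testing, and serious events are collected in any case. It is right that no primary or secondary efficacy result is affected.

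One could read the words pointing upward in 7.4 as meaning the list in 5.5. This is strained, because 7.3 comes immediately before and holds the only adverse event list in Section 7. Even so read, the questions would not match the risks that they are meant to mitigate.

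Two things survive these objections: the mismatch between the lists, and the gap for non-serious arrhythmias between 8.1 and 5.5.

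**Conclusion.** The point holds as an inconsistency with a practical consequence for safety ascertainment. The 7.4 statement is supported by the itemised daily list for 2 of 7 risks, or 3 of 7 with Section 8.1. No specific daily item for proximal myoneuropathy or suicidality is written in either document. If 5.5 and 8.1 are followed as written, non-serious arrhythmias can go unrecorded, which sits badly with the promise in Section 6.0. For the risks without an item, ascertainment is unspecific rather than absent.

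The conclusion assumes that the list above 7.4 is the one in 7.3, and that 5.5 describes the daily instrument fully. If the case report forms already contain the missing questions, the defect is confined to the protocol text. The documents give no event rates for these risks, so the number of events that might be missed cannot be estimated.

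**What to change.** Make 5.5, 7.3/7.4 and 8.1 agree.

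- Add a yes/no item on cardiac symptoms to the daily survey in 5.5. Section 8.1 already assumes that this information is collected.
- Add yes/no items for the other self-reportable 7.3 risks that 7.4 says are asked about: new muscle weakness and suicidal thoughts. List them in 8.1 with the other solicited events.
- State what the daily adverse event review in Appendices 1 and 2 asks.
- Reword 7.4 for the entries that a survey cannot cover (QTc prolongation) or that are handled by exclusion (psoriasis, porphyria).

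The cost is three short items on an existing survey, with the matching form and protocol changes. Positive answers also need a defined handling process, particularly for suicidal thoughts reported remotely; the investigators must set its content.

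The footnote to SAP Section 4.2.4 indicates that enrollment has ended. If data collection is complete, or the items are not added, correct the 7.4 statement and state in the safety reporting which package-insert risks were not specifically solicited, so that low counts are not read as evidence of absence. Correcting the sentence alone makes the document accurate but does not improve ascertainment.
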